7.1 Definition

7.1.1 Adverse Event

An adverse event (AE) is any untoward medical occurrence, unintended disease or injury, or untoward clinical signs (including abnormal laboratory findings) in subjects, users or other persons, whether or not related to the medical device under investigation.

This definition includes events related to the medical device(s) under investigation and the mapping/ablation procedures involved. For users or other persons, this definition is restricted to events related to the medical devices under investigation.

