7.1.2 Serious Adverse Event

If the AE meets any of the criteria below, it is regarded as a serious adverse event (SAE).

- a) Led to a death,
- b) Led to a serious deterioration in health of the subject, that either resulted in
 1. a life-threatening illness or injury, or
 2. a permanent impairment of a body structure or a body function, or
 3. in-patient hospitalization or prolongation of existing hospitalization, or
 4. medical or surgical intervention to prevent life threatening illness or injury or permanent impairment to a body structure or a body function.
 5. chronic disease
- c) Led to fetal distress, fetal death or a congenital abnormality or birth defect.

Note: A planned hospitalization for pre-existing condition, or a procedure required by the CIP, without a serious deterioration in health, is not considered to be an SAE.

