7.3 Adverse Event

7.3.1 Adverse Event Reporting

Safety surveillance and reporting starts as soon as the patient is enrolled in the clinical investigation. Safety surveillance and reporting will continue until the last follow-up visit has been performed, the subject is deceased, the subject concludes participation in the clinical investigation or the subject withdraws from the clinical investigation. Adverse event data, including deaths, will be collected

Clinical Investigation Plan

throughout the time period defined above and will be reported to the Sponsor on a CRF. Additional information with regard to an adverse event should be updated within the appropriate CRF.

Unchanged, chronic, non-worsening, or pre-existing conditions are not AEs and should not be reported.

An offline form will be made available to allow the investigator to report SAEs in the event the entry cannot be made in the EDC. This does not replace the EDC reporting system. All information must still be entered in the EDC system as soon as feasible.

Non-cardiac related abnormal laboratory values will not be considered AEs unless:

1. the investigator determined that the value is clinically significant,
2. the abnormal lab value required intervention, or
3. the abnormal lab value required subject withdrawal from the clinical investigation.

For the purposes of this clinical investigation, the following events will be reported:

- Adverse events that are considered to be related to any of the study devices or the mapping/ablation procedure by the investigator
- Serious adverse events resulting in death

Recurrence of AF, AFL, or AT are not considered reportable adverse events unless they occur in a severity, frequency, or other manner that is significantly worse than the subject's baseline condition. These are considered lack of effectiveness and will be reported as a recurrence on the appropriate case report form.

The investigator should report all SAEs to the Sponsor as soon as possible but no later than outlined below.

SAE Reporting

The investigator should report applicable SAEs to the Sponsor as soon as possible but no later than outlined below.

Clinical Site	Reporting timelines
All Sites	SAEs must be reported to the Sponsor no later than 3 calendar days from the day the site personnel became aware of the event or as per the investigative site's local requirements, if the requirement is more stringent than those outlined above.

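### Protocol 7.3.1 contradicts itself on which SAEs sites must report; non-fatal SAEs judged unrelated are in under some sentences and out under others

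*Protocol*

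**What the plan says.** Protocol 7.3.1 sets the scope of safety reporting in four places, in this order.

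1. A list introduced by "For the purposes of this clinical investigation, the following events will be reported". It has two items: "Adverse events that are considered to be related to any of the study devices or the mapping/ablation procedure by the investigator" and "Serious adverse events resulting in death".
2. A sentence after the paragraph on arrhythmia recurrence: "The investigator should report all SAEs to the Sponsor as soon as possible but no later than outlined below".
3. Almost the same sentence under the heading on SAE reporting: "The investigator should report applicable SAEs to the Sponsor as soon as possible but no later than outlined below". The protocol does not say what makes an SAE applicable.
4. The timeline table, which has one row for the whole study: "SAEs must be reported to the Sponsor no later than 3 calendar days from the day the site personnel became aware of the event". Stricter local rules take precedence over this limit.

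The definitions do not narrow the word SAE. Under Protocol 7.1.1 an adverse event counts "whether or not related to the medical device under investigation". Protocol 7.1.2 makes any adverse event serious if it meets one of the seriousness criteria, and relatedness is not among them.

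On the analysis side, Protocol 8.2 and SAP 3.2.4 both summarise adverse events as a categorical variable in the enrolled (ENR) population. Both describe them as including device-, procedure- and death-related events. That wording names these categories but does not confine the table to them.

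**The concern.** The list and the all-SAEs sentence cannot both be the full rule. Take a hospital admission during follow-up that the patient survives and that the investigator considers unrelated to any study device and to the procedure. It meets the SAE definition. Under the all-SAEs sentence and the timeline table the site must report it within 3 calendar days. Under the list it need not be reported at all.

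A site could follow either rule in good faith. If sites differ, the total SAE count and percentage would mix two definitions, and a difference between sites could reflect how 7.3.1 was read rather than what happened to patients. The plan has little that would reveal this:

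- SAP 3.3.2 plans no poolability analysis.
- Protocol 10.4 relies on central data review, with on-site monitoring at the sponsor's discretion. Central review may not detect an event that was never entered.
- Protocol 10.5 requires every deviation to be reported and allows no waivers. A site that follows the list complies with one sentence and breaches another.

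**Working it through.** The plan states no figure on this point, so the check compares the four rules by class of event.

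| Event class | Two-item list | All-SAEs sentence | Applicable-SAEs sentence | Timeline table |
|---|---|---|---|---|
| Fatal SAE | reported | reported | reported | reported |
| Non-fatal SAE judged related to device or procedure | reported | reported | reported | reported |
| Non-fatal SAE judged unrelated to both | **not reported** | **reported** | **undetermined** | **reported** |
| Non-serious AE judged related | reported | not addressed | not addressed | not addressed |
| Non-serious AE judged unrelated | not reported | not addressed | not addressed | not addressed |

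The rules conflict in one row only. Every fatal SAE and every related event has the same status whichever sentence a site follows. No visible text says which sentence governs.

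**Illustration of size.** The inputs are:

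- *N*, the number of subjects. The stated sample size is blacked out. Protocol 5.6 lets one centre enrol 20% of the maximum, given as about 60 subjects, so *N* ≈ 60 / 0.20 = 300.
- *p*, the share of subjects with at least one non-fatal SAE judged unrelated during follow-up. The documents give no value. I assume 2% to 20%.
- *f*, the share of subjects at sites that report all SAEs. This is unknown and lies between 0 and 1.

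The expected number of subjects reported with such an event is *N* × *p* × *f*, taking *p* to be the same at both kinds of site.

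- All sites follow the list (*f* = 0): 0 subjects.
- All sites report all SAEs (*f* = 1): 300 × 0.02 = 6 to 300 × 0.20 = 60 subjects.
- Half of subjects at each kind of site (*f* = 0.5): 300 × 0.02 × 0.5 = 3 to 300 × 0.20 × 0.5 = 30 subjects.
- One centre at its 60-subject limit: 60 × 0.02 = 1.2 to 60 × 0.20 = 12 subjects, in or out on that centre's reading alone.

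These are subjects, not events, since one subject can have several. When *f* lies between 0 and 1, the reported percentage for this class is *p* × *f*. That is neither the 0 of the narrow rule nor the *p* of the wide rule, because the denominator is everyone enrolled while the numerator comes only from sites on the wide rule.

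**The case against.** The strongest reply is that the section can be read as consistent. Only the list sets out to define scope; the two SAE sentences set timing. The second of them, under the SAE heading, speaks of applicable SAEs, which most naturally points back to the list. The all-SAEs sentence would then be a leftover duplicate. This is plausible and may be what was meant. But the protocol does not say so, and the reading leaves two items unexplained: the word *all*, and a timeline table that makes reporting mandatory for SAEs without a limit.

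It can also be said that training on the protocol and CRF completion is compulsory (Protocol 10.3), that the sample CRFs and the monitoring plan are available only on request, and that a blacked-out block follows the adverse event line in SAP 3.2.4. Any of these might settle the matter in practice. This stands: divergence between sites is possible, not shown.

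A reader might infer three stronger things, none of which the documents support.

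- *That device-safety or mortality counts are unreliable.* They are not affected by this conflict. Related events and deaths are reportable under every sentence, and these are the categories the SAP names.
- *That a known number of events will be lost.* No SAE rate is given, and the upper figures compare two extremes in which every site reads the section the same way.
- *That leaving relatedness to the investigator is part of the contradiction.* Protocol 7.2 openly assigns the device judgement to the investigator, and the list does the same for device and procedure. That is a design choice, and reconciling the sentences to the narrow rule would leave it as it is.

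**Conclusion.** Wrong as written: an internal inconsistency of minor severity. Protocol 7.3.1 gives incompatible scopes for SAE reporting, and the visible text does not resolve them. The effect is confined to non-fatal SAEs judged unrelated to device and procedure. Through that class, total SAE counts and percentages in the ENR adverse event table may vary with site practice.

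The illustrative ceiling of about 6 to 60 subjects rests on an assumed rate of 2% to 20% and on an enrolment of about 300 inferred from the centre limit. The contradiction does not depend on either figure. Adverse events are additional data, the SAP plans no hypothesis testing, and freedom from arrhythmia recurrence is not touched, which is why the severity is minor. This review takes no position on which reporting scope is right.

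**What to change.** - Reconcile the two-item list, the two SAE sentences and the timeline table into one reporting rule. If the word *applicable* is kept, define it.
- Carry that rule unchanged into the CRF instructions and site training.
- In the clinical report, state the scope that was applied and tabulate events under it. Show related events and deaths as a separate subset, since that subset is comparable across sites under either reading.
- If sites have already reported under different readings, establish which rule each followed before tabulating total SAEs.

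The cost is a protocol clarification with the matching change to CRF instructions and training. If the wider rule is kept, there are also some extra CRF entries. If sites have already diverged, there is the work of asking each one which rule it used.

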7.3.2 Device Complaint Reporting

The investigator is responsible for reporting all complaints to the manufacturer of a device that meets the definition of a complaint. A complaint is defined as any written, electronic or oral communication that

Clinical Investigation Plan

alleges deficiencies related to the identity, quality, durability, reliability, safety, effectiveness or performance of a device after it is released for distribution.

For Abbott products, the investigator must notify Abbott's Product Performance Group (PPG) by submitting the information on the device via email to [REDACTED] as soon as possible after becoming aware of the complaint. For non-Abbott products, the investigator must notify the manufacturer of the device per that manufacturer's complaint reporting mechanisms or per the investigator's user facility procedures. This information is not collected on a CRF for the study.

8.0 STATISTICAL CONSIDERATIONS

The following section describes the statistical methods for the clinical investigation.

8.1 Analysis Populations

[REDACTED]

[REDACTED]

[REDACTED]

[REDACTED]

8.2 Statistical Analyses

[REDACTED]

In general, continuous (CONT) variables will be summarized with the numbers of observations, means with standard deviations, quartiles, minimums, maximums, and 95% confidence intervals for the means as per the table mockups.

Categorical (CAT) variables will be summarized with subject counts and percentages/rates, and where specified in the table mockups, with exact 95% Clopper-Pearson confidence intervals.

Survival (SURV) analysis will be conducted to analyze time-to-event variables. Subjects without events will be censored at their last known event-free time point. Subjects withdrawn or otherwise lost-to-follow-up during the follow-up period will be censored at their last known visit. Survival data will be presented using the Kaplan-Meier product limit method.

Clinical Investigation Plan

The following lists describe the analysis methods for the additional evaluations that will be analyzed in the ENR population:

- LA volume and diameter (CONT)
- Adverse events including any device-, procedure-, or death-related events (CAT)
- Other baseline characteristics including but not limited to:
 - Time with AF (CONT)
 - Type of AF (CAT)
 - Sex (CAT)
 - BMI (CONT)
 - General medical history (CAT)
 - Cardiovascular history (CAT)
 - Arrhythmia history (CAT)
 - NYHA classification (CAT)
 - LVEF (CONT)
 - Presence of pacemaker (CAT)

The following lists describe the analysis methods for the primary endpoint and additional evaluations that will be analyzed in the PTE population:

This figure is a 2D grayscale heatmap or a processed image of a complex signal. It features a series of horizontal bands of varying intensities. The most prominent features are two large, dark, horizontal bands in the upper right quadrant, with a smaller, dark band extending downwards from the middle of the upper band. Between these dark bands are several lighter, horizontal bands. The entire structure is set against a white background and is rendered in black and white, giving it a high-contrast, almost binary appearance.

¹⁴ Difference in each measurement between the different mapping modes will be compared.

Clinical Investigation Plan

8.3 Sample Size Calculation and Assumptions

[REDACTED]

8.4 Timing of Analysis

Data analyses will be performed at the completion of the 12-month follow-up period for all subjects or as desired by Sponsor. In addition, study progress and data may be summarized and reported as needed.

8.5 Subgroup Analysis

No subgroup analyses are planned for this clinical investigation.

8.6 Multiplicity

[REDACTED]

8.7 Procedures for Accounting for Missing Data

Every effort will be made to collect all required data. [REDACTED]

[REDACTED]

8.8 Planned Interim Analysis

[REDACTED]

8.9 Statistical Criteria for Termination

There are no statistical criteria for termination of this clinical investigation.

8.10 Success Criteria

[REDACTED]

[REDACTED]

Clinical Investigation Plan

8.11 Deviations from Statistical Plan

Any changes to the planned statistical analyses will be documented in the final report.

9.0 DIRECT ACCESS TO SOURCE DATA/DOCUMENTS

The investigator/institution will permit direct access to source data/documents for the purpose of performing clinical investigation-related monitoring, audits, EC review and regulatory inspections.

Subjects providing informed consent are agreeing to allow clinical investigation monitors or regulatory authorities including foreign countries to review, in confidence, any records identifying the subjects in this clinical investigation. This information may be shared with regulatory agencies; however, Sponsor undertakes not to otherwise release the subject's personal and private information.

10.0 QUALITY CONTROL AND QUALITY ASSURANCE

10.1 Selection of Clinical Sites and Investigators

The Sponsor will select investigators qualified by training and experience to participate in the clinical investigation. Sites will be selected based upon review of a recent site assessment, if applicable, and the qualifications of the investigators who will participate in the clinical investigation.

10.2 CIP Amendments

Approved CIP amendments will be provided to the Investigators by the Sponsor prior to implementing the amendment. The Principal Investigator is responsible for notifying the EC or equivalent committee of the CIP amendment (administrative changes) or obtaining EC's approval of the CIP amendment (changes in subject care or safety), according to the instructions provided by the Sponsor with the CIP amendment.

Acknowledgement/approval by the EC of the CIP amendment must be documented in writing prior to implementation of the CIP amendment. Copies of this documentation must also be provided to the Sponsor.

Clinical Investigation Plan

10.3 Training

All Investigators and clinical investigation personnel are required to attend Sponsor training sessions, which may be conducted at an Investigator's meeting, a site initiation visit, or other appropriate training sessions. Over-the-phone or self-training may take place as required. Training of Investigators and clinical investigation personnel will include, but is not limited to, the CIP requirements, electronic case report form completion and clinical investigation personnel responsibilities. All Investigators and clinical investigation personnel that are trained must sign a training log (or an equivalent) upon completion of the training. Prior to signing the training log, Investigators and clinical investigation personnel must not perform any CIP-related activities that are not considered standard of care at the site.

10.4 Monitoring

It is the responsibility of the Sponsor to ensure the clinical study is conducted, recorded and reported according to the approved CIP, subsequent amendment(s), applicable regulations and guidance documents.

Centralized monitoring will occur through routine internal data review. This monitoring is designed to identify missing and inconsistent data, data outliers, and potential CIP deviations that may be indicative of site non-compliance. On-site monitoring may occur at the discretion of the Sponsor.

10.5 Deviations from CIP

The Investigator should not deviate from the CIP for any reason except in cases of medical emergencies when the deviation is necessary to protect the rights, safety and well-being of the subject or eliminate an apparent immediate hazard to the subject. In that event, the Investigator will notify Sponsor immediately by phone or in writing.

No waivers for CIP deviations will be granted by the Sponsor. All deviations must be reported to the Sponsor using the Deviation CRF. The occurrence of CIP deviations will be monitored by the Sponsor for evaluation of investigator compliance to the CIP and regulatory requirements and dealt with according to written procedures. Investigators will inform their EC or equivalent committee of all CIP deviations in accordance with their specific EC or equivalent committee reporting policies and procedures.

In the event of repeated non-compliance, as determined by the Sponsor, a Sponsor's monitor or company representative will attempt to secure compliance by one or more of the following (and not limited to):

- Visiting the investigator and/or delegate
- Telephoning the investigator and/or delegate
- Corresponding with the investigator and/or delegate

Repeated non-compliance with the signed agreement, the CIP or any other conditions of the clinical investigation may result in further escalation in accordance with the Sponsor's written procedures, including securing compliance or, at its sole discretion, Sponsor may terminate the investigator's participation in the clinical investigation.

Clinical Investigation Plan

10.6 Quality Assurance Audit

A Sponsor representative or designee may request access to all clinical investigation records, including source documentation, for inspection during a Quality Assurance audit.

In the event that an investigator is contacted by a Regulatory Agency in relation to this clinical investigation, the Investigator will notify Sponsor immediately. The Investigator and Research Coordinator must be available to respond to reasonable requests and audit queries made during the audit process. The Investigator must provide Sponsor with copies of all correspondence that may affect the review of the current clinical investigation (e.g., Form FDA 483, Inspectional Observations, Warning Letters, Inspection Reports, etc.). Sponsor may provide any needed assistance in responding to regulatory audits.

10.7 Committees

A Publication Committee may be established to oversee clinical investigations publications, including publication planning and authorship determinations. Publication Committee membership may include Principal Investigators, a representative of the Sponsor and a statistician. The Publication Committee will determine policy and strategies regarding individual presentations and/or publications arising from clinical investigation generated data. The committee will also review all external requests for accessing clinical investigation-related data and strategies aligning with the Sponsor's presentation and publication team expectations. The committee will also follow the Sponsor's applicable policies and Standard Operating Procedures.

11.0 DATA HANDLING AND RECORD KEEPING

Sponsor and/or its affiliates will maintain documentation of the systems and procedures used in data collection for the duration of the clinical investigation.

CRF data collection will be performed through a secure web portal and only authorized personnel will access the Electronic Data Capture (EDC) system using a unique username and password to enter, review or correct data. Passwords and electronic signatures will be strictly confidential.

The data will be subjected to consistency and validation checks within the EDC system and supplemental review by the Sponsor.

At the conclusion of the clinical investigation, completed CRF images with the date-and-time stamped electronic audit trail indicating the user, the data entered, and any reason for change (if applicable) will be provided to the investigational sites.

For the duration of the clinical investigation, the Investigator will maintain complete and accurate documentation including, but not limited to, medical records, clinical investigation progress records, laboratory reports, CRFs, signed ICFs, device accountability records (if applicable), correspondence with the EC and clinical investigation monitor/Sponsor, adverse event reports, and information regarding subject discontinuation or completion of the clinical investigation.

Clinical Investigation Plan

